	8. Delirium, based on one of the following criteria: Confusion Assessment Method (CAM) or CAM-ICU (even on 1 occasion), or Intensive Care Delirium Screening Checklist (ICDSC) >3, or 3DCAM, or 4AT ≥4, or more than one dose of haloperidol or similar antipsychotic drug, or documented delirium by neurologist or neurosurgeon or psychiatrist consultation (index hospitalisation).		
	9. Gut infarction confirmed by imaging (e.g. angiography), autopsy, or through surgical means (index hospitalisation).		

Page **13** of **55** IRAS ID: 325425

	10. Hospital visits (hospitalisation and/or emergency visits and coronary revascularisation at 6 months).				
	11. The proportion of patients transfused and the number of blood products utilised (RBCs, plasma, platelets) (index hospitalisation).				
	12. Seizures, defined as generalised or focal tonic-clonic movements consistent with seizure; or electroencephalogram (EEG) demonstrating epileptiform discharges; or diagnosis of seizures by neurologist or neurosurgeor consultation (index hospitalisation).				
	13. Encephalopathy, defined as unexpected delayed awakening or severely altered mental status (unconscious despite no sedative medication for more than 5 days), or encephalopathy documented by neurologist or neurosurgeon.				
Trial population	Patients at moderate to high risk of death (EuroSCORE I ≥ 6) that are 65 years of age or younger undergoing cardiac surgery on cardiopulmonary bypass (CPB).				
Trial design	Multi-centre, open-label, randomised controlled trial of a restrictive versus liberal transfusion strategy in higher risk patients ≤65 years of age having cardiac surgery on cardiopulmonary bypass, using a superiority trial design. A health economic analysis is embedded in the UK arm of the trial.				
	In the UK, an internal pilot including progression criteria has been built in, to assess whether the target number of UK centres within 9 months of green light, and recruitment rate of one participant per site per month, can be achieved.				
International sample size	1760 randomised participants in ~72 international sites.				
UK sample size	320 participants (160 per group) in 22 UK cardiac centres.				
Randomisation	Randomisation will have a 1:1 ratio, will be based on random permuted blocks of varying sizes, and will be stratified by centre and age.				

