**Outcomes:** The primary outcome is a composite of any of the following events within 6 months of the initial surgery: 1. All-cause mortality or 2. Myocardial infarction as defined by the 4th universal definition of myocardial infarction or 3. New onset renal failure with dialysis or 4. New focal neurological deficit (stroke). Secondary outcomes will include costs, quality of life, cost-effectiveness, and safety. Process and adherence will be monitored.

**Internal Pilot:** Planned site set-up and recruitment targets (1 participant/ site/ month), as well as methods for collection of healthcare resource use, will be tested in a 9 month internal pilot with prespecified Stop/ Go criteria.

**Sample Size:** The trial is powered to detect a Risk Ratio of 0.70 between groups at six-months. To achieve 90% power with  $\alpha$  =0.05, and with adjustment for an expected attrition rate of 4.5% and a single interim analysis, 1,802 participants (901 per group) are required.

Page **15** of **55** IRAS ID: 325425

**Analysis:** will follow a pre-specified statistical analysis plan in the intention to treat population. A cost utility analysis will be performed.

**Project timetable:** Start date: 1st February 2023. Months 1-7 set-up, months 8-30 recruitment, months 30 to 35 follow-up, months 34 to 36 data cleaning, site closedown.

**Dissemination:** We use the Knowledge Framework to focus on knowledge creation and dissemination to key stakeholders, including participants, clinicians, service users and commissioners.

Page **16** of **55** 

IRAS ID: 325425

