This trial will bring together the TRICS III research team in Canada with the TITRe2 team in the UK. Both of these trials were published in the New England Journal of Medicine and are widely cited in treatment guidelines. The TRICS IV trial aims to recruit 1760 participants from 72 units in 18 countries and is of sufficient size to definitively answer the research question. Inclusion of a large UK cohort will build on the experiences of the TITRE 2 and TRICS III researchers to increase generalisability of the trial results to NHS patients.

If the trial demonstrates that a liberal strategy is superior, the risks and costs of organ injury related to untreated severe anaemia will be reduced. If the liberal strategy is not superior, the risks and costs attributable to unnecessary transfusions will be reduced. The trial will thus provide high-quality generalisable data to guide transfusion practice worldwide, regardless of its eventual results.

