#### 16.1 Sample Size Estimation

TRICS IV is a superiority trial powered for the primary composite endpoint of all-cause mortality, myocardial infarction, new-onset renal failure with dialysis, or new focal neurological deficit (stroke), within 6 months after the initial surgery. A RR of 0.70, with an incidence rate for the primary endpoint of 14% in the liberal and 20% in the restrictive transfusion arm was used for the sample size calculation, which is in line with observed rates in the modified intention-to-treat (ITT) analysis of TRICS III in individuals younger than 69 years old. As observed in TRICS III, we assumed that 1.5% of the patients would be lost to follow-up by 6 months. With a 1:1 allocation ratio and a two-sided  $\alpha$ =0.05, we found that enrolment of a total of 1,440 patients (720 per group) would provide 85% power to detect a RR of 0.70 for the liberal as compared with the restrictive transfusion strategy while accounting for a 1.5% attrition rate and one interim analysis of the primary outcome. To ensure that the main analysis of the primary outcome has at least 80% power, we will conduct a conditional power analysis after 50% of the recruited participants have their primary outcome data available. If the conditional power is ≥60% but <80%, we will re-estimate the sample size needed so that the main analysis of the primary outcome has 80% power, and recruitment of participants will continue until the re-estimated sample size is reached. For all other values of conditional power, we will continue recruitment until the originally planned target sample size of 1,440 patients is reached.

We may include the first 100 randomised participants in an internal pilot assessment of the adherence to Hb triggers that utilize physiological changes for initiation of RBC transfusion.

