#### 16.4 Primary Outcome Analyses

The primary analysis of the primary outcome will be based on a chi-squared test. Superiority of liberal over restrictive transfusion will be declared with a p-value<0.05. A secondary analysis of the primary outcome will be based on a Cox regression model to derive hazard ratios (HR) with 95% confidence intervals, with the time to event presented per group using Kaplan Meier curves.

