#### 16.6 Interim Analyses

One interim analysis will be undertaken after 50% of patients have reached determination of the primary outcome. A group sequential design has been employed that applies a one-sided boundary. The boundary is based on a Hwang-Shih-DeCani spending function for efficacy. If the boundary is crossed, there will be a non-binding recommendation to stop the trial for benefit. We will only conduct additional safety reviews if otherwise directed by the Data and Safety Monitoring Board (DSMB). The following table shows the Z-statistics for the non-binding recommendation to stop the trial due to benefit.

Analysis	Z-statistic
Interim	2.75
Final	1.98

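### The protocol states three unreconciled recruitment targets (1,440, 1,760 and 1,802) with conflicting power and loss-to-follow-up assumptions

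*Protocol*

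**What the plan says.** Three totals for the international trial stand in the current text.

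- **Section 16.1 (Sample Size Estimation):** "we found that enrolment of a total of 1,440 patients (720 per group) would provide 85% power to detect a RR of 0.70". The assumptions are "an incidence rate for the primary endpoint of 14% in the liberal and 20% in the restrictive transfusion arm", one interim analysis and 1.5% loss by six months, a rate credited to TRICS III. The same section names 1,440 as the planned target, to which recruitment returns unless conditional power is at least 60% but below 80%.
- **Section 4 (Protocol summary):** "1760 randomised participants in ~72 international sites", with no power. Section 7.1 repeats it: "The TRICS IV trial aims to recruit 1760 participants from 72 units in 18 countries".
- **Section 5 (Scientific abstract):** for 90% power and a risk ratio of 0.70, "with adjustment for an expected attrition rate of 4.5% and a single interim analysis, 1,802 participants (901 per group) are required". Section 6 (Lay summary) also gives 1,802.

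Two other sections rely on the total without naming it. Section 16.6 says "One interim analysis will be undertaken after 50% of patients have reached determination of the primary outcome". Section 20 ends the trial once the specified number has been recruited and followed up, the database locked, and the results analysed and published.

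Section 18.1.2 gives TRICS III loss to follow-up for the primary outcome as 4.5% at 180 days, against the 1.5% that section 16.1 attributes to the same trial. The amendment history in section 24.3 lists no change to sample size, power or attrition, so none of these figures is marked as superseded.

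**The concern.** Target size, power and loss rate belong together as one design statement, and here they vary together across sections. A reader of the abstract expects 90% power from 1,802 patients. A reader of section 16.1 expects 85% from 1,440. A reader of the summary sees 1,760 and cannot tell what power it is meant to give.

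Three things are at stake. The first is the recruitment end point, because section 20 refers to a specified number and three are specified. The second is the number of patients who trigger the 50% look. The third is how the finished trial is read: in an open-label trial that stops at one of several published totals, the sponsor will be asked when that total was chosen. The loss rate matters separately, because both 1.5% and 4.5% are credited to TRICS III and each supports a different total.

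**Working it through.** **Inputs.** Event rates 20% (restrictive) and 14% (liberal), 1:1 allocation and a two-sided test (section 16.1); α = 0.05 (sections 5, 16.1 and 16.4); Z boundaries 2.75 interim and 1.98 final, with the look at 50% (section 16.6); loss 1.5% (section 16.1) or 4.5% (sections 5 and 18.1.2). The abstract does not restate the event rates, so 14% v 20% is assumed for it.

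**Step 1: reproduce 1,440.** With p̄ = 0.17 and difference 0.06, the pooled-variance formula per group is

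n = [1.960·√(2·0.17·0.83) + 1.036·√(0.20·0.80 + 0.14·0.86)]² / 0.06² = (1.0412 + 0.5488)² / 0.0036 = 702.3, so 703, or 1,406 in total.

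One look at half the information with boundaries 2.75/1.98 inflates this by 1.0084. Dividing by 0.985 for 1.5% loss gives 1,406 × 1.0084 / 0.985 = 1,439. The stated 1,440 reproduces.

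**Step 2: reproduce 1,802.** At 90% power, n = (1.0412 + 0.6786)² / 0.0036 = 821.6, so 822 per group and 1,644 in total. With the inflation factor for 90% power, 1.0080, and 4.5% loss: 1,644 × 1.0080 / 0.955 = 1,735, short of 1,802.

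A continuity correction, n′ = (n/4)·[1 + √(1 + 4/(n·0.06))]², raises 821.6 to 854.6, so 855 per group and 1,710 in total. Then 1,710 × 1.0080 / 0.955 = 1,805, within 3 patients of 1,802. The abstract's total is therefore also a coherent calculation, under a different power, loss rate and formula.

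**Step 3: power at each total.** With n evaluable patients per group, the final drift is θ = 0.06 / √(2·0.17·0.83/n). Power is the probability that the interim Z exceeds 2.75 or the final Z exceeds 1.98, where the two are bivariate normal with correlation √0.5.

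| Total | Evaluable per group at 1.5% / 4.5% loss | Power at 1.5% loss | Power at 4.5% loss | 50% of total |
|---|---|---|---|---|
| 1,440 | 709.2 / 687.6 | 85.0% | 83.9% | 720 |
| 1,760 | 866.8 / 840.4 | 91.2% | 90.3% | 880 |
| 1,802 | 887.5 / 860.5 | 91.8% | 91.0% | 901 |

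**Step 4: size of the conflict.** 1,802 − 1,440 = 362 patients, which is 25% of 1,440. Stated power differs by 5 points. The interim count differs by up to 901 − 720 = 181 patients.

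**Step 5: a possible origin of 1,760.** 1,440 + 320 (the UK sample) = 1,760. The protocol does not say that the middle figure arose this way, and it would not explain 1,802.

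**The case against.** The strongest reply is that section 16.1 is the design and the rest is unaligned front matter. That section holds the full derivation and names 1,440 as the fallback after the conditional-power analysis. Much of this stands. A reader might infer that the base for re-estimation is unspecified, but section 16.1 does specify it. What the reply does not settle is which total the trial recruits to, because nothing says that section 16.1 prevails over the summary. A trial recruiting to 1,760 or 1,802 would also exceed the section 16.1 fallback.

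A reader might also infer that the interim boundaries are wrong. The documents do not support this. At 50% of any single total the information fraction is 0.5, and 2.75/1.98 gives a one-sided type I error of 0.0251. A mismatch needs the interim to be timed on one total and the final analysis on another, which no section says. Even then, the error with the printed boundaries would only range from 0.0246 to 0.0254.

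Nor is the trial shown to be underpowered. On its own event rates, every total gives about 84% to 92% power, above the 80% floor in section 16.1. The defect is contradiction and not faulty arithmetic.

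**Conclusion.** The point holds as an internal inconsistency in figures that the trial relies on. Three recruitment targets, two power levels and two loss rates stand side by side in current text with no statement of which governs.

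If 1,440 governs, the abstract overstates power by 5 points (90% against 85.0%), or by about 6 points at the 4.5% loss that the abstract itself assumes (83.9%). If a larger total governs, section 16.1 understates the target by 320 or 362 patients and carries the wrong power, loss rate and fallback. The recruitment end point and the interim count follow whichever total applies.

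The power figures assume 14% v 20%, a pooled-variance test and the printed boundaries applied at half the information. The reproduction of 1,802 also assumes that those event rates underlie the abstract and that a continuity correction was used, which the abstract does not state.

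**What to change.** - In section 16.1, name one governing total with its power and one loss rate, and reconcile that rate with the TRICS III figure in section 18.1.2.
- Copy the total to the protocol summary, scientific abstract, lay summary and section 7.1.
- In section 16.6, give the resulting patient count beside the 50%.
- If 1,440 governs, restate the abstract's power as 85% (about 84% if 4.5% loss is kept) and remove 1,760 and 1,802.
- If a larger total already governs, correct section 16.1's total, power, loss rate and 1,440 fallback to match.

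The cost depends on the answer. With 1,440 it is a wording correction and a less favourable power statement in the abstract. With a larger total, the sample size section and the re-estimation rule change, which is a design amendment and should be recorded as such. The printed boundaries need no change in either case if the look stays at 50% of the named total.

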#### 16.2 Analysis population

The ITT population consists of all patients who underwent randomisation and subsequent cardiac surgery with available outcome data.

The per-protocol (PP) population consists of all participants who underwent randomisation and subsequent cardiac surgery with cardiopulmonary bypass with available outcome data, except for patients who had a protocol adherence of less than 90%, patients who were withdrawn from the trial by the treating physician at any time, and patients who withdrew consent.

#### 16.3 Baseline characteristics

The baseline characteristics of the patients will be summarised by group. Continuous variables will be summarised using mean and standard deviation, or median and inter-quartile range if data do not have a symmetric distribution. Categorical variables will be summarised with counts and percentages. No statistical comparisons of participant characteristics at baseline will be performed between groups.

#### 16.4 Primary Outcome Analyses

The primary analysis of the primary outcome will be based on a chi-squared test. Superiority of liberal over restrictive transfusion will be declared with a p-value<0.05. A secondary analysis of the primary outcome will be based on a Cox regression model to derive hazard ratios (HR) with 95% confidence intervals, with the time to event presented per group using Kaplan Meier curves.

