#### 10.3 Randomisation Procedure

Randomisation will be performed by the delegated research nurse/enroling physician using a centralised web-based system (REDCap) generated by the Applied Health Research Centre (AHRC) at the Li Ka Shing Knowledge Institute of St. Michael's Hospital, Unity Health Toronto. UK sites will use this system to enter relevant data to enable randomisation of participants in the UK. Access to the randomisation system will be managed by the AHRC following completion of necessary training.

Randomisation will have a 1:1 ratio, will be based on random permuted blocks of varying sizes, and will be stratified by centre and age. We will use web-based electronic case report forms (eCRFs), which can be accessed by each site, to randomly allocate participants to interventions. Each participant will be assigned a unique participant ID at enrolment. This unique participant ID will be used to identify the individual participant throughout the trial and will not be reassigned to any other participant.

Whenever feasible, randomisation will occur no more than 24 hours prior to the scheduled surgery to minimise the risk of losing randomised patients due to unplanned surgery cancellations. This timeline is only a guideline and it is not considered a protocol deviation to randomise > 24 hours before surgery.

Page 23 of 55

IRAS ID: 325425

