#### 16.8 Sensitivity Analysis

We will fit a random-effects model that accounts for the variation between sites in the between group difference of the primary composite outcome. We will also conduct an analysis of the primary composite outcome adjusted for variables that have a clinically significant difference between groups at baseline. In additional sensitivity analyses, we will determine whether analyses of specific patient subsets, as defined below, yield similar results for the primary outcome:

- 1. Excluding patients with any non-adherence to the assigned transfusion strategy
- 2. Excluding patients whose haemoglobin was never measured below 95g/L from the time of randomisation to the end of the index hospitalisation period
- 3. Excluding patients who did not receive any RBC transfusions from the time of randomisation to the end of the index hospitalisation period
- 4. Excluding patients who had at least one protocol suspension from the time of randomisation to the end of the index hospitalisation period
- 5. Excluding patients randomised according to physiologic triggers
- 6. Including only patients of the PP population

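### The primary chi-squared test ignores the randomisation strata and is mildly conservative, and the adjusted sensitivity analysis picks its covariates by observed baseline imbalance

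*Protocol*

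**What the plan says.** - Section 10.3: randomisation is 1:1 and "will be based on random permuted blocks of varying sizes, and will be stratified by centre and age". The summary and the scientific abstract name the same two factors.
- Section 16.4: "The primary analysis of the primary outcome will be based on a chi-squared test", and "Superiority of liberal over restrictive transfusion will be declared with a p-value<0.05". The secondary Cox model names no strata or covariates.
- Section 16.8: two further analyses of the overall effect in all patients. One is a random-effects model for between-site variation in the treatment difference. The other is "adjusted for variables that have a clinically significant difference between groups at baseline", with no list of variables and no threshold.
- Section 16.7: a model with eight covariates named in advance, age among them, used only for exploratory subgroup and interaction estimates.
- Section 16.5: adjusted logistic regression for secondary outcomes, covariates not named.
- Section 16.3: no statistical comparison of the arms at baseline.

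**The concern.** Two things look wrong.

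1. Stratified permuted blocks remove centre and age differences from the contrast between arms. An unadjusted chi-squared test still counts that variation as error. If centre and age predict the outcome, the standard error used is somewhat too large, so the p-value is too large and some power is lost.

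2. The adjusted analysis in 16.8 lets the data choose the model. Because 16.3 rules out baseline tests, the choice is a judgement made after baseline data by arm have been seen, in a trial without blinding of treatment. Section 18.1.2 mentions masking the statistician only for the interim. The rule also picks variables that happen to differ, not variables that predict outcome. Centre and age are balanced by design, so it will tend to leave out the two factors that the design most clearly calls for. A reader could not tell whether the adjusted estimate would have been the same under a model named in advance.

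**Working it through.** **Inputs from the protocol (16.1, 16.6).** "an incidence rate for the primary endpoint of 14% in the liberal and 20% in the restrictive transfusion arm"; "With a 1:1 allocation ratio and a two-sided" alpha of 0.05; "we assumed that 1.5% of the patients would be lost to follow-up by 6 months"; 1,440 patients for 85% power; one interim analysis with a final Z of 1.98. The protocol states other totals elsewhere; 1,440 is used because 16.1 derives it.

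**Step 1: reproduce the sample size for the unadjusted test.**
n per arm = [1.960 × √(2 × 0.17 × 0.83) + 1.036 × √(0.20 × 0.80 + 0.14 × 0.86)]² / 0.06² = 703.
Dividing by 0.985 and doubling gives 1,428. With 1.98 in place of 1.960, n = 712 and the total is 1,446. The stated 1,440 lies between them. With 720 × 0.985 = 709 evaluable per arm, power is 85.3%, and about 85% with both looks counted. So the stated figure holds for the test as planned.

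**Step 2: cost of ignoring balanced prognostic strata (normal approximation).** Let the balanced factors shift the log-odds with standard deviation SD (assumed; the protocol gives none).
- R² = 1 − E[p(1 − p)] / (0.17 × 0.83), where p is the stratum risk averaged over arms.
- True type I error of the chi-squared test = 2Φ(−1.96 / √(1 − R²)).
- Power = Φ((0.06 − 1.96 × SE) / SE₁), where SE₁ is the true standard error with strata balanced. SE is √(2 × 0.17 × 0.83 / 709) = 0.01995 for chi-squared, and this × √(1 − R²) for the adjusted analysis.

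For SD 0.5: R² = 0.034, adjusted SE = 0.01961, SE₁ = 0.01954. Chi-squared: (0.06 − 0.0391) / 0.01954 = 1.070, power 85.8%. Adjusted: (0.06 − 0.0384) / 0.01954 = 1.104, power 86.5%.

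| Assumed SD | R² | True type I error, chi-squared | Power, chi-squared | Power, adjusted | Total with the same precision |
|---|---|---|---|---|---|
| 0.2 | 0.006 | 4.9% | 85.4% | 85.5% | 1,432 |
| 0.3 | 0.012 | 4.9% | 85.5% | 85.8% | 1,422 |
| 0.5 | 0.034 | 4.6% | 85.8% | 86.5% | 1,391 |
| 0.7 | 0.064 | 4.3% | 86.2% | 87.6% | 1,347 |
| 1.0 | 0.122 | 3.7% | 86.9% | 89.5% | 1,265 |

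The last row would need strong patient-level predictors; it is not a plausible value for centre and age alone.

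**Step 3: simulation.** 1,440 patients, 72 centres, two age strata (assumed), permuted blocks, 20,000 runs per case.

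| Centre SD / age log-odds ratio (assumed) | Type I error, chi-squared | Type I error, stratified Mantel-Haenszel | Power gain at Z 1.98 |
|---|---|---|---|
| 0.3 / 0.4 | 4.9% | 5.1% | 0.1 points |
| 0.5 / 0.6 | 4.5% | 5.0% | 0.6 points |
| 0.7 / 0.8 | 4.0% | 4.9% | 1.9 points |

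A separate run with 4,000 replicates per case (Monte Carlo error about 0.6 points for power) showed no difference in the first case and gains of about 1.0 and 2.4 points in the other two. With equal age strata the combined SDs are √(0.3² + 0.2²) = 0.36, √(0.5² + 0.3²) = 0.58 and √(0.7² + 0.4²) = 0.81. The formula in step 2 then gives type I errors of 4.8%, 4.5% and about 4.0%, which agrees.

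**Step 4: the selection rule in 16.8.** No arithmetic applies. The four relevant statements are the adjustment rule (16.8), no baseline tests (16.3), open-label allocation (10.4) and stratification by centre and age (10.3). Together they leave an undefined judgement made with allocation known, and one unlikely to select the stratification factors.

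**The case against.** The case for leaving the plan alone is substantial.

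- **The chi-squared test is valid, and the trial is sized for it.** This stands. A reader might infer that type I error is inflated or that the trial is underpowered; step 1 and the tables show neither.
- **The gain is small and rests on assumptions.** This stands. The protocol gives neither the prognostic strength of centre or age nor the number of age strata. Section 7.3 presents age as a modifier of the treatment effect, which does not say how strongly it predicts outcome.
- **Adjustment is planned elsewhere.** A reader might infer that the imbalance rule is the only fixed-effect covariate adjustment in the protocol. Section 16.7 contradicts that, and 16.5 plans adjusted logistic regression too. But 16.7 serves only exploratory subgroup estimates, so neither supplies an adjusted overall effect on the primary outcome.
- **A sensitivity analysis cannot change the declared result.** Correct: superiority rests on the chi-squared p-value. What is at risk is the credibility of a supportive estimate.
- **Covariate lists belong in the analysis plan.** Often so, and 18.1.2 promises a published one. But the protocol does not leave the matter open: it states an unadjusted test and an imbalance-based rule.
- **Stratification will be sparse.** With 72 centres and two assumed age strata, 1,440 / 144 = 10 patients and about 1.7 events (at 17%) per stratum. Strata with one arm or no events add nothing. Hence a pooling rule is needed.

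**Conclusion.** The point holds as an improvement in efficiency and coherence, not as a failure of validity. The primary test ignores both stratification factors and is mildly conservative: true type I error about 4-5% and about 0-2 points of power forgone. Both figures depend on assumed prognostic strengths, and the stated 85% power stands either way.

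The stronger part is 16.8. The adjusted sensitivity analysis of the overall effect selects covariates after the fact, on imbalance, without a list or threshold, and no named overall-effect analysis adjusts for age.

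A larger gain might be inferred from adjusting for EuroSCORE I. With an assumed binary-scale R² of 3.6% to 9.0%, 1/(1 − R²) − 1 gives about 4-10% more effective sample size. A test stratified by centre and age would not deliver that; only a covariate model would, and the R² values have no source in the protocol.

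**What to change.** Before unblinded data are examined:

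1. **16.4:** make the primary test account for the randomisation strata. One option is a Cochran-Mantel-Haenszel test with the Mantel-Haenszel risk ratio and risk difference, stratified by centre and randomisation age stratum. The risk ratio also matches the scale of the planning target of 0.70. State in advance how small centres are pooled, for example within country below a given size.
2. **16.6:** use the same statistic at the interim as at the final analysis.
3. **16.8:** keep the crude chi-squared test as a sensitivity analysis. Replace the imbalance-based selection with a fixed list of prognostic covariates already collected, for example age, EuroSCORE I, preoperative haemoglobin, surgery type and centre.

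The sample size need not change and no new data are needed. The cost is a protocol amendment, which must be international because one coordinating centre analyses the whole trial, plus the pooling rule. Recruitment began in October 2021 and the protocol does not say whether the interim has taken place, so the amendment should be written by people who have not seen outcomes by arm.

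### Section 16.4 tests the final primary outcome at an unadjusted p<0.05 (Z 1.96), while section 16.6 sets a group-sequential final boundary of Z 1.98 (p<0.0477); a small mismatch that needs one sentence

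*Protocol*

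**What the plan says.** Three sections of the protocol bear on the final test of the primary outcome.

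- **Section 16.4 (Primary Outcome Analyses)** names the test, "The primary analysis of the primary outcome will be based on a chi-squared test", and then the criterion, "Superiority of liberal over restrictive transfusion will be declared with a p-value<0.05". It does not mention the interim analysis or any adjustment of the p-value.
- **Section 16.6 (Interim Analyses)** plans one look at the primary outcome at 50%, with a one-sided efficacy boundary. On the type of boundary it says "The boundary is based on a Hwang-Shih-DeCani spending function for efficacy". The parameter of that function is not given. The boundary table is introduced by "The following table shows the Z-statistics for the non-binding recommendation to stop the trial due to benefit" and lists 2.75 for the interim and 1.98 for the final analysis.
- **Section 16.1 (Sample Size Estimation)** uses a two-sided alpha of 0.05 and "an incidence rate for the primary endpoint of 14% in the liberal and 20% in the restrictive transfusion arm". It concludes "we found that enrolment of a total of 1,440 patients (720 per group) would provide 85% power to detect a RR of 0.70", "while accounting for a 1.5% attrition rate and one interim analysis of the primary outcome".

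**The concern.** A chi-squared p below 0.05 corresponds to |Z| above 1.96, and the tabulated final boundary is 1.98. These are two thresholds for one test, and no sentence says which governs or describes the p-value in 16.4 as sequentially adjusted.

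A group-sequential design raises the final critical value because some of the type I error is spent at the interim. Testing at 1.96 after an interim look that could itself yield an efficacy claim takes the overall error above the planned level. The practical risk is a borderline result. A final Z between 1.96 and 1.98 would leave the headline claim open to argument after unblinding, which a pre-specified rule is meant to prevent.

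**Working it through.** **Inputs.** Section 16.6: interim Z 2.75, final Z 1.98, look at 50%, one-sided boundary. Section 16.1: two-sided alpha 0.05 (0.025 one-sided), event rates 14% and 20%, 1.5% attrition, 720 per group, 85% power. Section 16.4: p<0.05. Assumption: the Hwang-Shih-DeCani parameter γ is not stated, and −4 is inferred below.

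**1. Reproduce the boundary table.** Error spent by information fraction t is α(1−e^(−γt))/(1−e^(−γ)). With α=0.025, t=0.5 and γ=−4:

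- Interim: 0.025×(1−e²)/(1−e⁴) = 0.025/(1+e²) = 0.00298, so Z = 2.750.
- Final: solve P(Z₁<2.75, Z₂<c) = 0.975 for a bivariate normal with correlation √0.5. This gives c = 1.981.

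Both match the table. Neighbouring values do not: γ=−5 gives 2.895 and 1.972, and γ=−3.5 gives 2.678 and 1.988. The two-sided nominal p at 1.98 is 2×(1−Φ(1.98)) = 0.0477.

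**2. Reproduce the sample size.** Use a pooled-variance two-proportion test with the two boundaries, 85% power, and division by 0.985 for attrition.

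| Design | Evaluable per arm | After attrition, per arm | Total |
|---|---|---|---|
| 2.75 then 1.98 | 708.2 | 719.01, rounded up to 720 | 1,440 |
| 2.75 then 1.96 | 699.0 | 709.6, rounded up to 710 | 1,420 |
| No interim, 1.96 | 703 | 714 | 1,428 |

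The figure in 16.1 matches the design with 1.98.

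**3. Type I error under each rule.** This step uses only the stated Z values, so γ is not needed. If an interim crossing counts as success, one-sided error is 1 − P(Z₁<2.75, Z₂<c).

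| Final rule | One-sided error | One-sided interim, two-sided final |
|---|---|---|
| Z≥1.98 (16.6) | 0.0251 | 0.0489 |
| Z≥1.96 (16.4) | 0.0262 | 0.0512 |

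The 0.0251 differs from 0.025 only because 1.981 is rounded to 1.98. A simulation with 5 million draws gave one-sided values of 0.0250 and 0.0261. If an interim crossing never counted and only the final test decided, the one-sided error at 1.96 would be 0.025. The range for the 16.4 rule is therefore 0.0250 to 0.0262.

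**4. Power.** Evaluable per arm: 720×0.985 = 709. With 2.75 then 1.96, power is 85.49%; with 2.75 then 1.98, it is 85.04%. The difference is 0.45 points.

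**5. How often the two rules disagree.** In favour of liberal, with no interim crossing, the chance of a final Z between 1.96 and 1.98 is 0.02618−0.02506 = 0.0011 under the null. Under the planned effect it is 0.8549−0.8504 = 0.0045.

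**The case against.** The strongest reply is that 16.6 labels its table as a recommendation to stop, and a non-binding one. It nowhere says that a final Z below 1.98 means superiority has not been shown. A reader might infer that 16.6 states an explicit failure rule; it does not, and 1.98 as the success threshold is an inference. The inference is a strong one. A value for the final analysis cannot advise stopping, and the sample size fits it. The non-binding wording also explains why 0.0262 is an upper bound: it counts every interim crossing as a success. It does not restore 1.96, because the protocol permits a stop for benefit and nowhere rules out an efficacy claim at the interim.

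A second reply is that the analysis plan promised in section 18.1.2 will set the nominal level. It may, but the protocol has already stated two different values, so this is a contradiction and not a detail left for later.

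Two stronger readings are tempting and should be set aside.

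- Doubling 0.0262 gives 5.24%. That assumes a symmetric interim boundary for harm, whereas 16.6 has a one-sided boundary for benefit. The figure for this design is 5.12%.
- Because a chi-squared p-value has no sign, one might say that 16.4 would call liberal superior even if it had more events. The wording of 16.4, the directional hypothesis in 7.8, the objective in 8.1 and the one-sided boundary in 16.6 all make the intended direction clear.

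**Conclusion.** The mismatch is real. Section 16.4 uses 1.96 for a test whose boundary table and sample size both point to 1.98. Type I error under 16.4 is at most 0.0262 one-sided against 0.025, or about 5.12% in total against 5%, on the assumption that an interim crossing can count as success. The error figures rest on the stated boundaries and a look at 50% information; only the reproduction of the table depends on the inferred γ of −4.

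The size makes this a minor correction and not a must-fix. Design, enrolment and data collection are unaffected, and the two rules would rarely disagree. The reason to act is that the criterion for the only primary outcome should be single-valued before unblinding. Nothing here shows what the final boundary should be after the sample-size re-estimation in 16.1; that was not examined, and 1.98 should not be assumed to carry over.

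**What to change.** Amend 16.4 to say that, at the final analysis, superiority of liberal is declared if the test statistic in favour of liberal is at least 1.98 (two-sided nominal p<0.0477). In 16.6, state the Hwang-Shih-DeCani parameter, with the sponsor confirming whether it is −4, so that the final boundary can be recomputed if the interim does not fall at 50% information.

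The change is one sentence in 16.4 and one number in 16.6. It needs no extra participants. Relative to testing at 1.96 it gives up about 0.45 points of power, and the 85% stated in 16.1 is kept.
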